### 1.3 Clinical Trial Data

In a Phase I trial of intravenous ascorbic acid in patients with advanced malignancy the high-dose intravenous ascorbic acid was well tolerated when administered to patients. Adverse events and toxicity were minimal at all dose levels. Ascorbic acid concentrations reached up to 25 mmol/L in patients who received ascorbic acid of 1.5 g/kg. Of the 24 patients in the study, only 4 recorded minor adverse events including headache, dizziness and diarrhea. In another phase I trial using pharmacological ascorbate concurrently with gemcitabine in patients with locally advanced and

metastatic pancreatic cancer conducted at University of Iowa Hospitals and Clinics, 9 patients received treatment. Individual doses between 50 to 125 g per infusion were given for maintenance of 350 mg/dL level in plasma. 75-g dose yielded peak plasma levels ranging between 320 and 630 mg/dL. No dose limiting toxicities or serious adverse events were reported.

A phase I study of adding ascorbate to standard therapy in glioblastomas and NSCLC was initiated in 2013. Subjects were assigned to high-dose ascorbate dose cohorts for the concomitant portion of therapy. Dose cohorts ranged from 15g to 87.5g. During the adjuvant phase, subjects underwent interpatient dose escalation to achieve a targeted plasma ascorbate level of 350 mg/dL. Subjects received high-dose ascorbate during the adjuvant phase for up to 6 cycles. To date, 5 subjects have been enrolled in the recommended phase 2 dose of 87.5g. Treatment was well-tolerated with minimal adverse events. No subject experienced a grade 3 or greater hematologic or non-hematologic toxicity. The only adverse events associated with ascorbate were grade 1 dry mouth, grade 1 chills, and grade 2 hypertension. Dry mouth is transient and ends shortly after infusion. Grade 1 chills are infusion related, most likely due to the volume of fluid infused. Grade 2 hypertension occurs in some subjects during infusion, again most likely due to the volume of fluid infused.

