## 5. TREATMENT PLAN AND STUDY SCHEMA

### 5.1 Study Design

This is a single-arm open-label phase Ib/II clinical study assessing the efficacy of concurrent high dose ascorbate in combination with radiotherapy in patients with locally advanced, resectable, high grade sarcomas, as measured by pathological response rates. Patients will be treated with three times weekly IV ascorbate concurrently with radiation therapy. Surgery will be performed 4-6 weeks from the end of radiation therapy to allow for resolution of acute toxicities per current standard of care.

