### 5.2 Phase Ib

The phase Ib portion of this study is to ensure the safety and tolerability of high dose ascorbate in combination with EBRT as assessed by incidence of dose-limiting toxicities (DLT). Although this combination has been shown to be safe and well tolerated in GBM, this combination has not been studied in sarcoma patients. EBRT will be given at the standard dose for resectable soft tissue sarcomas according to the NCCN sarcoma guidelines. Patients will receive 50 Gy over 25 fractions for extremity and trunk sarcomas or 45 – 50.4 Gy in 28 fractions for retroperitoneal sarcomas, during which time they will be receiving three times a week IV high dose ascorbate. IV ascorbate infusions will be continued until the end of radiation therapy. Surgery will be performed 4-6 weeks from the end of radiation to allow for adequate tissue healing and resolution of acute toxicities.

Ascorbate will be dosed at an initial dose of 75gm IV three times a week concurrently with radiation therapy provided patient tolerated the test dose of ascorbate during screening without any reactions. Initially 3 patients will be entered at the Dose 0 for ascorbate and be monitored at this three times a week dose until surgery when safety issues will be addressed. Otherwise, ascorbate dose will be deescalated and dose -1 will be explored as outlined. For this protocol DLT will be defined as an attributed adverse event (definite, probable or possible) that meets the criteria (Section 6.3).

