## Ascorbate Dose Levels

[figure not shown]
Dose 0      Ascorbate 75 gm IV three times weekly concurrently with radiation  
Dose -1      Ascorbate 62.5 gm IV three times weekly concurrently with radiation  
•      Initial dose for all = Ascorbate 75gm IV

## 5.3 Phase 2

[figure not shown]
The phase 2 part of the study will provide an estimate of the relative treatment effect of pharmacological ascorbate in combination with preoperative EBRT in subjects with locally advanced, resectable, extremity or retroperitoneal high grade sarcomas, as measured by pathological response rates.

As above, patients will receive the first dose of pharmacological ascorbate intravenously on day 1 of week 1 provided no reactions are seen to the test dose. This will be followed by 3 times a week dosing (= 15 doses total) at Dose 0 until completion of EBRT. Standard doses of radiation for resectable soft tissue sarcomas according to the NCCN sarcoma guidelines will be administered. Patients will receive preoperative radiation at a dose of 50 Gy over 25 fractions for extremity and trunk sarcoma or 45 to 50.4 Gy in 28 fractions for retroperitoneal sarcomas starting on week 1 day 1. Subjects should be followed either by clinic visit or phone contact every 12 weeks (+/- 4 weeks) for approximately 24 months after the end of the treatment phase, at which time the initial survival data and disease recurrence will be assessed. Details as per study calendar (Section 10).

[figure not shown]

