## 5.6 Concomitant Ascorbate (High-dose Ascorbic Acid) Infusions

5.6.1 **Participant dose.** All patients will receive a standard ascorbate dose of 75 gm given over 120 minutes

5.6.2 **Administration.** Based on subject tolerance; infusion rate should not exceed 500 mL/hour without consulting with physician. Recommended infusions times are as follows (Table 1) but may be adjusted for subject comfort. Changes in infusion rates should be recorded.

5.6.3 **Initiation.** Start the week prior to chemoradiation with one 15-g infusion. This is the test dose. 75 gm dosing begins week 1 of radiation therapy. If the participant fails the 15g test dose it is not considered dose limiting toxicity.

5.6.4 **Schedule.** Scheduled three times weekly during chemoradiation;

5.6.5 **Duration.** Subjects will continue with therapy until the end of standard radiation therapy or if any criteria of removal are met (Section 5.7)

5.6.6 **Dose modifications.** Provided in Section 6.2

**Table 1.** Recommended Infusion Times for Pharmacological Ascorbate †

Ascorbate dose (500 mg / mL)	Total volume*	Osmolarity (mOsm/L) §	Infusion Time
15g (30 mL)	250 mL	681	30 minutes
75g (150 mL)	1000 mL	851.7	120 minutes
62.5 g (125 mL)	1000 mL	709	120 mins

† Provided by Drug Information Center at the University of Iowa, July 2011

\* Sterile water for injection only. Do not use D5W

§ Theoretical calculations provided by Drug Information Center; targeted osmolarity range is 500 – 900 mOsm/L

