## 6.3 Dose Limiting Toxicities

### Definitions of dose-limiting toxicity:

Toxicity will be evaluated according to CTCAE version 5.0. DLT will be defined as any of the following ascorbate related toxicity or related to the combination of pharmacologic ascorbate and radiation therapy during treatment and up to 28 days after the first pharmacologic ascorbate infusion:

- Infection grade 4
- SAE per 21CFR312.21 with an attribution of *possible, probable, or definite* to ascorbate
- Grade 3 diarrhea or nausea/vomiting despite maximal support
- Any grade 3/4 or greater hematologic or non-hematologic toxicity not explainable by another cause in the opinion of the principal investigator, with the exceptions of:
  - Expected radiation related skin toxicity of any grade.
  - Brief (< 1 week) grade 3 fatigue.

If unexpected DLT occurs, ascorbate administration should be delayed until the DLT has resolved to at least CTCAE version 5.0 grade 1 or baseline and future dose be reduced to dose level -1 as per table 1. If dosing is delayed by more than 4 weeks due to the occurrence of unexpected adverse event or if a patient already dose reduced to level -1 (62.5 gm/dose) experiences another DLT that is considered related to ascorbate, then the subject should be taken off study.

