## 10. STUDY CALENDAR

### 10.1 Study Procedures

	Screen b	Treatment a					Off treatment and end of study c	Follow Up d
		Week 1	Week 2	Week 3	Week 4	Week 5 (+1wk j )		
H & P	X	X		X		X		
Tumor biopsy (optional)	X b							
Performance status	X						X	X
Clinical MRI/ Staging CT	X						X	X e
Pregnancy test k (urine)	X							
G6PD	X							
EKG	X							
CBC w/diff	X			X		X		
PT/INR, PTT & uric acid	X							
Height	X							
Weight, BSA	X						X	
Vitals (BP, pulse) m	X	X	x	X	x	X	X	
Comprehensive metabolic panel (CMP)	X	X		X		X	X	
Ascorbate infusion	X i	XXX	XXX	XXX	XXX	XXX		
Blood for ascorbate levels f	X	X		X		X		
ROS Research blood g	X	X		X		X	X	
Immunology research lab g	X					X	X	
Iron Panel including ferritin h	X						X	
T2* /QSM and DWI MR imaging sequences (optional)	X			X			X	
Adverse Events & Con Meds			X	X	X	X	X	

**a** study day 1 is defined as radiation therapy day 1 (i.e., fraction 1).

**b** screening labs, history, and physical must be obtained  $\leq$  28d from d1. G6PD may be obtained at any time prior to test dose. MRI/CT obtained  $\leq$  28d from d1 (RT sim is acceptable). Pregnancy test per institutional guidelines. Optional tumor biopsy can be done anytime before week 1 dosing.

**c** includes both off-treatment evaluation and study completion. Study completion requires a final study dictated visit 4 to 6 weeks after the last dose of ascorbate. Follow at least monthly until resolution of all ascorbate related adverse events.

**d** approx every 3 months (every 12 weeks [+/- 4 weeks]) for overall survival through passive chart review, phone call or scheduled follow-up visit for 2 years

**e** Imaging as per standard of care for site specific sarcomas

**f** 4cc green-top Na-Heparin tube. Draw pre-infusion at 15g dose, then 30 min post-infusion: week 1 day 1 , week 3 and last infusion of week 5

**g** 6cc pink-top EDTA tube. Draw pre infusion The specimen should be placed on ice immediately after draw and carried to the lab

**h** At time of screening and end of study

**i** Test dose of 15 g intravenously once G6PD levels confirmed to be adequate. A physician must review the patient's medication list against the list of medications prohibited on this trial prior to the test dose of ascorbate.

**j** In case of radiation treatment delays due to holidays

**k**  $\pm 7$  days prior to day 1

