## 12. STATISTICAL CONSIDERATIONS

### 12.1 Phase Ib

The primary objective of the Phase Ib portion of this study is to confirm the current standard dose of intravenous ascorbate, 75 gm, utilized in patients diagnosed with pancreatic cancer also receiving concurrent chemo radiation is safe within this population of sarcoma patients being treated concurrently with pre-operative radiation. Up to six (6) patients will be recruited to the standard dose, 75 grams administered intravenously 3 times a week during radiation therapy (5 weeks). If at most 1 out of 6 patients experience a DLT, the standard dose will be considered safe. If 2 or more patients experience a DLT, the next cohort of patients will be assigned to dose level - 1. The recommended phase II dose (RP2D) will be defined as the highest dose level for which at most 1 out of 6 patients experience a DLT.

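### Section 6.3 runs the 28-day DLT clause from the first infusion, so completers have no DLT observation after treatment, out of step with 5.2, which monitors the first three patients until surgery

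*Combined protocol and SAP*

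**What the plan says.** Section 6.3 limits DLTs to related toxicity occurring "during treatment and up to 28 days after the first pharmacologic ascorbate infusion". The other dates that matter are these:

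- Section 5.3 gives the "first dose of pharmacological ascorbate intravenously on day 1 of week 1", and note a to the calendar in 10.1 makes study day 1 the day of fraction 1.
- On duration, 5.6.5 says: "Subjects will continue with therapy until the end of standard radiation therapy". Section 5.3 gives a total of 15 doses.
- Section 5.1 places surgery "4-6 weeks from the end of radiation therapy to allow for resolution of acute toxicities".
- Section 5.2 has the first three patients "monitored at this three times a week dose until surgery when safety issues will be addressed". Its next sentence provides for de-escalation otherwise, and it then refers to 6.3 for the DLT criteria.
- Section 12.1 sets the decision rule without naming any window: "If at most 1 out of 6 patients experience a DLT, the standard dose will be considered safe". The de-escalation table in 5.2 and 6.2 names none either.
- Adverse events are collected for 30 days after the last dose (Appendix D; 7.5 for serious events). Note c in 10.1 adds: "Study completion requires a final study dictated visit 4 to 6 weeks after the last dose of ascorbate".

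**The concern.** A DLT window normally covers some time after the last dose, because that is when exposure is complete. Here the fixed period runs from the first dose, so it expires while the patient is still being treated. The patients with the most exposure get the least observation after dosing.

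The count of at most 1 in 6 is the rule that clears 75 gm, and under 12.3 it would open that dose to about 19 further patients (25 - 6). Section 5.2 links the review at surgery to de-escalation, so a reader of 5.2 would expect events up to surgery to bear on the dose. A reader of 6.3 would leave them out of the count.

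What is at stake is narrow. Expected radiation skin toxicity is exempt under 6.3, and wound complications after surgery lie outside every window considered here. That leaves serious events attributed to ascorbate, grade 4 infection, and other related grade 3/4 events arising between the end of treatment and surgery.

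**Working it through.** **Inputs.** Three infusions a week for 5 weeks (12.1); 25 or 28 fractions (5.2); first full dose on day 1 (5.3, 10.1 note a); surgery 28 to 42 days after radiation (5.1, 5.2). Assumptions: weekday fractions starting on a Monday, and infusions on Monday, Wednesday and Friday.

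**The plan's own figure.** 3 × 5 = 15 doses, as 5.3 states. Dose 15 falls on day 33.

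**End of treatment.** Fraction 25 is the Friday of week 5: 4 × 7 + 5 = day 33. Fraction 28 is the Wednesday of week 6: 5 × 7 + 3 = day 38.

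**End of the 28-day clause.** 1 + 28 = day 29. That is 4 days before the end of 25 fractions and 9 days before the end of 28, so the clause adds nothing for a completer.

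**Who it helps.** A patient off all treatment after week 1 has the last infusion on day 5 and is observed for 29 - 5 = 24 days after it. A 25-fraction completer is observed for 33 - 33 = 0 days.

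**Other readings.** If both conditions had to hold, the window would close on day 29. If the first infusion meant the 15 g test dose, taken as 7 days before day 1, the clause would end about day 22. Neither reading gives observation after treatment.

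**Days before surgery that fall outside the count:**

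| Last infusion / end of radiation | Surgery | Uncounted now | Last infusion + 28 | Uncounted then | AE collection ends (+30) |
|---|---|---|---|---|---|
| day 33 / 33 | day 61-75 | 28-42 days | day 61 | 0-14 days | day 63 |
| day 38 / 38 (17 doses, per 5.6.5) | day 66-80 | 28-42 days | day 66 | 0-14 days | day 68 |
| day 33 / 38 (stops at dose 15) | day 66-80 | 28-42 days | day 61 | 5-19 days | day 63 |

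The third row takes treatment in 6.3 to include radiation. A one-week radiation delay, with ascorbate continuing to its end, moves both ends equally and leaves the 28 to 42 days unchanged.

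**Effect on the decision, with no rate assumed.** One uncounted event changes the result only if exactly one other patient has a counted DLT. Uncounted events in two patients change it whenever at most one DLT is counted.

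**Illustration only.** Let p be the true DLT rate up to surgery and f the share of DLTs falling inside the window. Then P(at most 1 of 6) = (1 - pf)^6 + 6pf(1 - pf)^5. The documents give neither p nor f.

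| p | f = 100% | 90% | 75% | 50% |
|---|---|---|---|---|
| 5% | 0.967 | 0.973 | 0.981 | 0.991 |
| 10% | 0.886 | 0.905 | 0.931 | 0.967 |
| 20% | 0.655 | 0.704 | 0.776 | 0.886 |

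**The case against.** The strongest reply is that the text is coherent as written. Section 6.3 can be read as covering the whole of treatment, with a 28-day minimum for anyone who stops early. Section 5.2 speaks of monitoring and a safety review at surgery; it never says that DLTs are counted until then. On that reading 6.3 defines the event and 5.2 sets how long the first three are watched. This stands, and it rules out two stronger inferences that a reader might draw. One is that 5.2 and 6.3 flatly contradict each other; they do not. The other is that the word first is a slip for last; that is possible, but nothing in the documents shows it.

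The evidence in 1.3 also points to small consequences. One trial had 4 of 24 patients with minor events, the pancreatic trial had no DLT in 9 patients, and of the glioblastoma and lung cancer study the protocol says: "No subject experienced a grade 3 or greater hematologic or non-hematologic toxicity". The ascorbate effects described in that last study came during or shortly after infusion, which 6.3 covers. This is not DLT timing, and combined toxicity with radiation could come later, but it gives no support for a large uncounted share.

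Late events are not lost. They are recorded for 30 days, ascorbate-related ones are followed at least monthly to resolution (10.1 note c), and the monitoring committee reviews trends. If 5.2 also means that accrual waits for the review at surgery, which it does not say outright, late events in the first three would be seen before expansion, and the gap would matter mainly for the second three. None of these safeguards puts an event into the count, however, and the only listed stopping rule in Appendix D is treatment-related death.

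**Conclusion.** The point holds as a misalignment between sections. As written, completers have no DLT observation after treatment, and the 28 to 42 days before surgery are monitored under 5.2 for the first three patients but fall outside the 6.3 window that feeds the dose decision. The calendar result rests on the weekday schedule assumed above.

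The effect on the decision is unknown, because the documents give neither a DLT rate nor its timing. At a 5% rate the chance of clearing the dose moves from 0.97 to at most 0.99 even if half of DLTs are missed. It becomes material only at rates such as 20% (0.66 to 0.89), which 1.3 does not suggest. A reader might infer that 75 gm would be cleared unsafely; the documents do not support that. The change is worth making because it is cheap and the count is what opens Phase 2.

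**What to change.** In 6.3, define the DLT window as running from the first full-dose infusion (75 gm, or 62.5 gm at dose -1) until 28 days after the last ascorbate infusion, and state that the 15 g test dose does not start it. Refer to this window in 5.2 and 12.1. Make the 3- and 6-patient decisions only when every patient in the cohort has completed the window or had a DLT.

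No patients or visits are added. The window closes 2 days inside the existing 30-day event collection, and the off-treatment visit is already 4 to 6 weeks after the last dose. For the first three patients it closes no later than the earliest surgery date, where 5.2 already places the review.

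The costs are as follows:

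- The second-cohort decision comes about 4 weeks later than at end of treatment. If accrual waits, that is about 2 patients (28 days at 2 per month, or 1.8).
- The calendar lists no CBC after week 5, so late hematologic events depend on clinical draws unless one is added at the off-treatment visit.
- The gap narrows but does not close: 0 to 14 days before surgery stay uncounted, or 5 to 19 if ascorbate stops at dose 15 of a 28-fraction course.

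Running the window to the off-treatment visit, where adverse events are already collected, or to surgery is an acceptable alternative. Serious-event collection would then need to be aligned, since surgery can fall as late as day 75 to 80 and the 30-day period ends on day 63 to 68.

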**Table 1. Phase 1b Dose De-escalation Schedule**

Number of Patients with DLT at a Given Ascorbate Dose	Decision Rule
$\geq 2$	Dose level will be declared toxic. If this is the lowest dose level, stop the study due to excessive toxicity; otherwise enter three additional patients at the next lowest dose level.
$\leq 1$ out of 3	Enter three more patients at this dose level.
$\leq 1$ out of 6	This is the recommended dose for the subsequent Phase2.

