## 5.9 Criteria for removal from study

Treatment with pharmacological ascorbate may be discontinued if any one of the following criteria is met:

- Intercurrent illness that prevents further administration of treatment,
- Unacceptable adverse event(s),
- Patient decides to withdraw from the study, or
- General or specific changes in the patient's condition render the patient unacceptable for further treatment in the judgment of the investigator
- Progressive disease as determined by the investigator
- A female subject becomes pregnant or fails to use 2 highly effective methods of contraception (for those subjects who are able to conceive).
- A female subject breast feeds while on study treatment.
- A male subject fails to use a highly effective method of contraception

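### The DLT definition exempts expected radiation skin toxicity at every grade, so a grade 4 or higher in-field reaction put down to radiation can go uncounted in the Phase 1b dose decision

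*Combined protocol and SAP*

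**What the plan says.** Section 6.3 counts toxicity related to ascorbate, or to ascorbate combined with radiation, in a window defined as "during treatment and up to 28 days after the first pharmacologic ascorbate infusion". It lists four kinds of DLT:

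- grade 4 infection;
- a serious adverse event with possible, probable or definite attribution to ascorbate;
- grade 3 diarrhea or nausea/vomiting despite maximal support;
- grade 3/4 or greater toxicity "not explainable by another cause in the opinion of the principal investigator".

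Only the last carries exceptions. One is "Expected radiation related skin toxicity of any grade". The other is "Brief (< 1 week) grade 3 fatigue", which is bounded in both grade and duration.

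The dose decision uses the number of patients with a DLT and nothing else. Table 1 in Sections 5.2 and 6.2 says of a dose with at most 1 DLT in 6: "This is the recommended dose for the subsequent Phase2". Section 12.1 agrees: "If at most 1 out of 6 patients experience a DLT, the standard dose will be considered safe".

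Skin is followed elsewhere. Section 3.2 makes skin toxicity over the tumor a secondary objective. Section 12.2 reports grade 3-4 dermatitis with an exact confidence interval. Neither is tied to the dose decision. The only stopping or pausing trigger in Appendix D is a treatment-related death.

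**The concern.** Section 1.2 gives ascorbate its place in this trial partly because it enhanced the radiation sensitivity of sarcoma cells in the laboratory. If some of that effect reached normal tissue in the field, a worse skin reaction is one direct way it could show, and it would look like ordinary radiation toxicity. The DLT definition is meant to capture toxicity of the combination, yet its general grade criterion sets this type of event aside at any severity.

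Prior experience does not settle the matter. Section 5.2 says: "Although this combination has been shown to be safe and well tolerated in GBM, this combination has not been studied in sarcoma patients". Section 1.3 reports no grade 3 or greater toxicity in the glioblastoma and lung cancer study, which is reassuring but concerns other tumor sites.

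At stake is the label placed on 75 g. If all six Phase 1b patients are treated at that dose and it passes, Section 12.3 adds 25 − 6 = 19 patients at it.

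**Working it through.** **Routes by which an in-field skin event can become a DLT**

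| Route | Covers skin? | Depends on |
|---|---|---|
| Grade 3/4 or greater toxicity (6.3) | Only if not expected or not radiation related | Investigator's judgment; no grade boundary for expected |
| Serious adverse event (6.3, defined in 7.5) | Yes, no skin exception | Seriousness, and at least possible attribution to ascorbate |
| Grade 4 infection (6.3) | Yes, no skin exception | The event being an infection |

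Section 5.7.11 lists in-field erythema and desquamation as anticipated, without grades, so it sets no severity limit on what is expected. Section 7.3 treats an event as unexpected if its severity is not listed, but that definition serves FDA reporting and is not carried into 6.3. The words on grade in the exception point the other way.

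What escapes is therefore narrow: a grade 4 or higher in-field reaction of a listed type that is not an infection and is either not serious or attributed to radiation and not even possibly to ascorbate.

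**Price of closing the gap**

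The plan states no operating characteristic for the Phase 1b rule. Its one power statement concerns Phase 2 (Section 12.2: 25 patients, at least 6 responders, 10% versus 30%). It reproduces: exact one-sided level 0.0334 and power 0.8065, against the stated 0.03 and 81%. This point does not change it.

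For Phase 1b, a dose fails when 2 or more of 6 patients have a DLT. With per-patient DLT probability p,

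P(fail) = 1 − (1 − p)^6 − 6p(1 − p)^5.

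Looking first at three patients, as in Table 1 of Section 5.2, gives the same value, because 2 DLTs in the first three already fail the dose.

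Let o be the rate of other DLTs and s the rate of grade 4 or higher in-field skin events, independent of each other. Counting the skin events gives p = 1 − (1 − o)(1 − s). All values of o and s are assumptions.

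Example, o = 0.10 and s = 0.02:

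- Now: 1 − 0.9^6 − 6(0.1)(0.9^5) = 1 − 0.5314 − 0.3543 = 0.1143.
- With the fix: p = 1 − 0.90 × 0.98 = 0.118, and 1 − 0.4708 − 0.3779 = 0.1513.

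| Other DLTs (o) | P(fail) now | s = 1% | s = 2% | s = 5% |
|---|---|---|---|---|
| 5% | 3.3% | 4.5% | 5.9% | 10.9% |
| 10% | 11.4% | 13.2% | 15.1% | 21.2% |
| 20% | 34.5% | 36.4% | 38.4% | 44.2% |

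The added failure is 1.2 to 3.9 points at s of 1% to 2%, and 7.7 to 9.8 points at 5%. Under independence these are upper figures, because they treat every grade 4 or higher skin event as newly counted, whereas some already count as attributed serious events.

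**Why the cap belongs at grade 3 and not lower**

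If every grade 3 or higher skin event counted, skin alone would fail a dose with probability 11.4%, 34.5% or 58.0% at assumed grade 3 or higher rates of 10%, 20% or 30%. That could reject 75 g for reactions that radiation causes by itself.

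**The case against.** The best case for the plan is that a limit exists already, set by seriousness and not by grade. The serious-event criterion has no skin exception and needs only possible attribution. Section 7.5 defines serious broadly, including hospitalization, life-threatening events and important medical events, and Section 7.1 requires an ascorbate attribution for every event of grade 3 or higher. There are also discretionary checks: safety review at surgery (5.2), stopping ascorbate for unacceptable events (5.9) and review of trends by monitors (Appendix D). And since radiation alone causes skin reactions and there is no control arm, counting them may blame ascorbate for radiation's effect.

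Much of this stands. A reader might infer that skin toxicity can never be a DLT, or that its severity has no limit at all. The documents support neither: attributed serious events, grade 4 infections and unexpected skin events all count. Some exemption is a fair choice.

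What remains is attribution. The serious-event route asks about ascorbate, while the lead-in to 6.3 asks about ascorbate or the combination. A severe reaction put down to radiation fails the first question and is exempt from the general criterion that could have answered the second. The discretionary checks set no skin threshold for the dose decision.

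A reader might also infer that the DLT window always closes with treatment. It does so for a patient who completes about five weeks, since day 28 has then passed. For one who stops earlier, it runs to 28 days after the first infusion.

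**Conclusion.** The point holds as a modest gap in the DLT definition. An in-field reaction of grade 4 or higher that the principal investigator attributes to radiation, and not to ascorbate, can leave the DLT count unchanged and 75 g regarded as safe. Many such events will be caught as attributed serious adverse events, so the gap is smaller than the wording of the exception first suggests.

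Its size cannot be computed, because the documents give no skin toxicity rate. The failure probabilities price the remedy and do not measure harm. They rest on assumed rates and on independence between skin events and other DLTs. Nothing in the documents shows that ascorbate worsens skin reactions or that 75 g is unsafe, and a reader should not infer either. The Phase 2 sample size and primary analysis are unaffected. This is a change worth considering because it is cheap and specific.

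**What to change.** In Section 6.3, change the exception to: expected radiation-related skin toxicity up to grade 3. Add one sentence: a grade 4 or higher in-field skin event in the DLT window counts as toxicity of the combination unless the principal investigator documents a cause other than radiation or the ascorbate-radiation combination.

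The editing cost is one changed line and one added sentence, with no new data collection. The real cost is the higher chance that a dose level fails, as tabulated in the working, including some failures due to radiation alone. Grade 3 reactions stay exempt, and the change does not reach events that begin after the DLT window closes.

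A descriptive table of grade 3 or higher in-field skin events at the Phase 1b safety review is optional. Without a threshold it would not change the decision rule, so it is not part of the fix.
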